#### **9.4.2. Secondary Analyses**

##### **Efficacy**

The major secondary endpoint in this study is the change from baseline in the average volume voided per micturition at week 12 after the first treatment.

This will be analyzed using MMRM as well as the primary endpoint. This model will include the treatment group, a stratification factor, site, visit, and treatment-by-visit interaction as fixed factors, baseline values and baseline-by-visit as covariates. An unstructured variance structure will be used to model the within-subject errors, shared across treatments. Analysis will be done with the MIXED procedure in SAS®, using the Kenward-Roger option to estimate denominator degrees of freedom and standard errors. Significant tests will be based on least-squares means using a two-sided 5% significance level (two-sided 95% confidence intervals). The dataset including only data until week 12 after the first treatment will be used for MMRM.

The following endpoints until week 12 after the first treatment will be analyzed using MMRM. This model will include the same factors as the model for major secondary endpoint. The treatment differences after week 12 after the first treatment will be analyzed using analysis of covariance (ANCOVA) model at each visit. This model will include the treatment group, site and a stratification factor as fixed factors, and baseline values as a covariate. Note that for daily average number of urinary incontinence episodes and daily average number of urinary urgency incontinence episodes, MMRM and ANCOVA will not include a stratification factor as fixed factors because the strong correlation is expected between baseline values and a stratification factor.

- Change from baseline and percent change from baseline:
  - Daily average number of urinary incontinence episodes (except for change from baseline at week 12 after the first treatment)
  - Average volume voided per void (except for change from baseline at week 12 after the first treatment)
  - Daily average number of urinary urgency incontinence episodes
  - Daily average number of voids
  - Daily average number of urgency episodes
  - Daily average number of nocturia episodes (voids that interrupt night sleep)
- Change from baseline

- Daily average number of urgency episodes by each urgency intensity category
- Maximum urgency intensity

The following endpoints will be analyzed using ANCOVA model at each visit. This model will include the treatment group, site and a stratification factor as fixed factors, and baseline values as a covariate.

- Change from baseline
  - Overactive Bladder Symptom Score (OABSS) total score
  - King's Health Questionnaire (KHQ) domain score

The following endpoints will be analyzed by using the Cochran-Mantel-Haenszel test stratified by a stratification factor. Missing data will be imputed by multiple imputation strategy.

- Proportion of subjects attaining 100%,  $\geq 75\%$  and  $\geq 50\%$  reduction from baseline in the daily average of urinary incontinence episodes
- Proportion of subjects attaining 100%,  $\geq 75\%$  and  $\geq 50\%$  reduction from baseline in the daily average of urinary urgency incontinence episodes
- Proportion of patients with positive response on the TBS

Duration of treatment effect will be evaluated for each treatment group in 2 different ways.

- Time to the subject's first request for 2nd treatment from the day of 1st treatment (regardless of fulfilment of the re-treatment criteria)
- Time to the subject's first qualification for 2nd treatment from the day of 1st treatment

The time to event will be graphically displayed as Kaplan-Meier curves. The endpoints will be tested using a log-rank test stratified by a stratification factor. Time to request/qualification for 2nd and 3rd treatment will not be analyzed.

No adjustment for multiplicity will be made for major secondary endpoint and other secondary endpoints.

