## **9.4. Key Elements of Analysis Plan**

### **9.4.1. Primary Analyses**

The primary endpoint in this study is the change from baseline in the daily average number of urinary incontinence episodes at week 12 after the first treatment.

This will be analyzed using a mixed model for repeated measures (MMRM). This model will include the treatment group, site, visit, and treatment-by-visit interaction as fixed factors, baseline values and baseline-by-visit as covariates. An unstructured variance structure will be used to model the within-subject errors, shared across treatments. Analysis will be done with the MIXED procedure in SAS®, using the Kenward-Roger option to estimate denominator degrees of freedom and standard errors. Significant tests will be based on least-squares means using a two-sided 5% significance level (two-sided 95% confidence intervals). The dataset including only data until week 12 after the first treatment will be used for MMRM.

Sensitivity analysis under the assumption of missing not at random for missing data will be performed, because MMRM is valid only under the assumption of missing at random. This will be documented in RAP.

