## **Safety**

All AEs that occur during the study will be recorded and classified using the current Medical Dictionary for Regulatory Activities (MedDRA). Events will be summarized overall, by treatment cycle and for the first 12 week of 1st treatment phase ( $\leq 84$  days from 1st treatment). Frequencies of AEs will be presented by system organ class and preferred term. Summaries of treatment-related AEs (study drug-related and injection procedure-related), AEs leading to discontinuation, AEs by intensity, and SAEs also will be provided.

ANCOVA for change from baseline in PVR urine volume will be performed at each visit. This model will include the treatment group, site and a stratification factor as fixed factors, baseline PVR urine volume as a covariate. The proportion of patients who will have a change from baseline in PVR

category (urine volume of < 100 mL, ≥ 100 to < 200 mL, ≥ 200 to < 350 mL, and ≥ 350 mL) will be summarized by visit.

The proportion of subjects using CIC (for urinary retention or elevated PVR) post-treatment will be summarized by PVR category. Time to start of CIC from most recent treatment, duration of CIC and PVR volume at the time of initiation of CIC will be also presented.

The observed value of clinical laboratory test and its change from baseline will be summarized by treatment group. The number of subjects with values outside of normal range by visit will be tabulated by treatment group to evaluate the changes in clinical laboratory tests.

The observed value of vital signs and changes from baseline will be summarized by treatment group. Also the ECG findings by visit will be summarized by treatment group.

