7.3.4. Strategy for Intercurrent (Post-Randomization) Events

For binary data, DO=NR rule will be applied to missing data until 12 weeks after 1st treatment. For categorical data for maximum urgency intensity, baseline observed carried forward will be applied missing data until 12 weeks after 1st treatment. For time to event data, missing data will be treated as censor. All missing data for other secondary endpoints not mentioned above are treated as missing, will not be imputed, unless otherwise specified.

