
 If the response to the diary question of "How would you rate your need to urinate?" is missing, then do; 
 If the response to the diary question of "Was this episode associated with a sudden and urgent need to urinate?" is "Yes", the above response will be imputed as "3-Severe Urgency". If the response to the diary question of "Was this episode associated with a sudden and urgent need to urinate?" is "No", the above response will be imputed as "0-No Urgency". If the response to the diary question of "Was this episode associated with a sudden and urgent need to urinate?" is missing, the above response will be treated as missing. If the response to the diary question of "Record volume collected OR indicate "not collected" for each episode" is missing, then this response will be treated as missing, not zero of volume. 		

Diary Data Convention

 As for other response, the missing response will be treated as missing. In other words, this is the same meaning to be treated as "No" to the response to the diary question.
Handling of missing urinary time

 For diary data with a diary date but missing the urinary time, the diary time will be set to mid-day at 12:00 pm at that day.
Handling of partial missing day in diary

 Partial missing day is defined as any missing diary day or invalid diary day in 3-day period. If there are 1 or 2 partial missing days in 3- day bladder diary, these days will be treated as missing and no imputation will be done for partial missing day. Therefore, endpoints in 3- day bladder diary will be calculated by using 1 or 2 valid diary data, if there is any partial missing day in the visit.
Definition of Incomplete 3-day diary

 Incomplete 3-day diary is defined as the diary which does not have 3 valid diary days.

KHQ and OABSS Convention				
Derivation of KHQ domains				
Following table shows the derivation of KHQ domains [Committee for Preparation of the Clinical Guideline for Overactive Bladder, the Japanese Continence Society, 2015]. Only role limitations and social limitations will be analysed by ANCOVA model. Other domains will be only summarized.				
Domain	ITEMS	Question in eCRF	scale	Derivation

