	Less than once a week	1
	Once a week or more	2
	About once a day	3
	2-4 times a day	4
	5 times a day or more	5
•		
Handling of partial missing data		

 • If missing data exists in KHQ and OABSS data in the visit, the corresponded item or domain will be treated as missing. 		

TBS
Answers and positive response of TBS

TBS (treatment benefit scale) consists of 4 answers to 1 questions "Please complete the following question by considering your current condition (urinary problems, urinary incontinence) compared to your condition before you received any study treatment in this trial". Subjects will select their answer to this question considering their condition. Available answers are below and will be coded 1 to 4 in order to use statistical analysis.
 
 • 1 - Greatly improved • 2 - Improved • 3 - Not changed • 4 - Worsened 
The answers of 1 – Greatly improved or 2 – Improved will be regarded as positive response.
 
Other answers including missing data will be regarded as NO positive response.

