Controlled imputation	
 This imputation will be based on missing not at random assumption, and done as sensitivity analysis for primary endpoint and major secondary endpoint. This will be applied for sensitivity analyses of primary endpoint and major secondary endpoint until week 12 after first treatment. For both endpoints, multiple imputations will be done for change from baseline. Imputation model for current missing data will include the previous observed or imputed data, treatment and baseline covariates. 
 For primary endpoint, baseline covariate is the baseline daily average number of urinary incontinence episodes as continuous. For major secondary endpoint, baseline covariates are baseline UUI episodes over 3-day diary (<= 9 or >= 10) and baseline average volume voided per micturition as continuous. In controlled imputation methods, Imputation of missing data will be imputed by following procedure (Mallinkckrodt (2013)). Missing data will be filled in using 100 different sets of values which results in 100 imputed datasets. 
 From non-monotone missing dataset to monotone missing dataset: to use MCMC partial imputation. Initialization. Set t=0 (baseline visit) Iteration. Set t=t+1. Create a data set combining records from placebo and GSK1358820 treated subjects with columns for baseline covariates and outcomes at visit 1,...,t with outcomes for all GSK1358820 treated subjects set to missing at visit t and set to observed or imputed values at visit 1,...,t-1 (Note that in this study, multiple imputation will be done for week2, week6 and week12. This means visit 0 (baseline visit), 1 (week2), 2 (week6) and 3 (week12) in this study). Imputation. Run Bayesian regression in SAS PROC MI on this data to impute missing values for visit t using previous outcomes for visits 1 to t-1 and baseline covariates. Note that only placebo data will be used to estimate the imputation model because no outcome is available for

CONFIDENTIAL

204947

Element	Reporting Detail

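### Up to Week 12, OABSS, two KHQ domains and PVR are analysed by observed-case ANCOVA at each visit, while the diary change endpoints use MMRM, and no reason is given

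*Protocol*

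**What the plan says.** Protocol 9.4.2 (Efficacy) introduces the list of diary endpoints with "The following endpoints until week 12 after the first treatment will be analyzed using MMRM". By-visit ANCOVA is kept for visits after Week 12. The next list, OABSS total and KHQ domain scores, has no such split: "The following endpoints will be analyzed using ANCOVA model at each visit". Under Safety, the same section says "ANCOVA for change from baseline in PVR urine volume will be performed at each visit".

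The SAP (both versions) follows this. Section 7.3.5.1 gives OABSS and KHQ, for all visits, the model defined for the diary endpoints after Week 12. Section 11.6.3 narrows the KHQ tests: "Only role limitations and social limitations will be analysed by ANCOVA model". Section 8.5.1 applies ANCOVA to PVR in the first treatment cycle, with an estimate and confidence interval but no p-value.

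On missing data, SAP 7.3.4 states: "All missing data for other secondary endpoints not mentioned above are treated as missing, will not be imputed, unless otherwise specified". None of the exceptions named there covers OABSS or KHQ. No imputation is specified for PVR. Controlled imputation (SAP 11.7.3) is "done as sensitivity analysis for primary endpoint and major secondary endpoint" only. The list of changes in SAP 2.1 does not mention the difference in models, and neither document explains it.

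**The concern.** At Weeks 6 and 12 the plan treats similar longitudinal data in two ways. The MMRM uses a subject's earlier visits when Week 12 is missing. A separate Week 12 ANCOVA does not, so a subject seen at Week 6 but not in the Week 12 window contributes nothing to the Week 12 contrast. Observed-case ANCOVA is unbiased if missingness depends only on terms in its model. It is biased if missingness depends on the interim response, which is not in the model. The MMRM remains valid there under missing at random, the assumption the plan already makes for its primary analysis; Protocol 9.4.1 adds a sensitivity analysis "because MMRM is valid only under the assumption of missing at random".

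Re-treatment is the natural reason for by-visit ANCOVA later in the study. It cannot explain the choice up to Week 12, because Protocol 5.3 requires at least 84 days since the previous injection. At stake are the Week 12 treatment differences for the patient-reported scores and the Week 12 PVR estimate.

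**Working it through.** **Plan's own figures.** The plan states no power, effect or dropout for OABSS, KHQ or PVR. Its stated power (98%, 91%, joint at least 89%; Protocol 9.2.1) reproduces by the two-sample t-test at 97.6%, 91.1% and 97.6 + 91.1 - 100 = 88.7%. These figures do not bear on this point.

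**Inputs, all assumed.** Outcomes are on a standardised scale with residual SD 1, higher being worse.
- Week 6 and Week 12: y = -0.5·treatment + 0.3·baseline + error, with correlation 0.5 or 0.7 between the two errors.
- Dropout after Week 6: logit(p) = c + s·y6, with c set so that overall dropout is 5%, 10% or 20%. The slope s is 0, 1 or -1 by arm.
- 400,000 subjects per arm, so the noise in a difference is about √(2/400,000) = 0.002 SD.

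**Estimators.**
- Observed-case ANCOVA: the treatment coefficient from y12 on treatment and baseline, among subjects with y12.
- MMRM equivalent for two visits with monotone dropout: b_trt + b_y6·g. Here b_trt and b_y6 come from y12 on treatment, baseline and y6 among completers, and g is the treatment coefficient for y6 in all subjects.

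**Bias of the Week 12 ANCOVA, in SD (range over correlation 0.5 to 0.7; positive means toward zero):**

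| Dropout depends on Week 6 response | 5% | 10% | 20% |
|---|---|---|---|
| Not at all | within 0.003 of 0 | within 0.003 of 0 | within 0.003 of 0 |
| Equally in both arms | 0.011–0.017 | 0.017–0.026 | 0.024–0.035 |
| In placebo only | 0.026–0.036 | 0.052–0.069 | 0.094–0.132 |
| In opposite directions by arm | 0.046–0.069 | 0.092–0.130 | 0.171–0.241 |

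The MMRM bias was within 0.004 SD of zero in every cell.

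**Scale.** With 120 per arm the standard error of a difference is about √(2/120) = 0.129 SD. With equal dependence and 5% to 10% dropout, the bias is 0.011/0.129 = 0.09 to 0.026/0.129 = 0.20 standard errors, or 2% to 5% of the assumed effect (0.011/0.5 to 0.026/0.5).

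**Trial-size check.** This used 120 per arm, a true effect of -0.40 SD and correlation 0.7. Active subjects were missing at random (5%, 10%, 15%). Placebo subjects were missing at 2%/8%, 5%/15% and 5%/25% below/above the median Week 6 score. Two runs gave observed-case estimates of -0.379 and -0.387, -0.366 and -0.369, and -0.334 and -0.343, which is 3% (0.013/0.40) to 17% (0.066/0.40) too small. The MMRM-type estimates lay between -0.396 and -0.402, with standard errors 1% to 4% smaller.

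**The case against.** The strongest reply is that the dropout needed for a large bias runs against the design. Re-treatment with active drug opens at the Week 12 visit to qualifying subjects of either arm (Protocol 4.6.2, 5.3), so a poor placebo responder has a reason to stay. This stands, and it makes the placebo-only and opposite-direction rows the less likely ones.

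A withdrawal visit can also fill the Week 12 slot: Day 65 to 106 for efficacy and, if the scheduled value is missing, Day 78 to 92 for safety (SAP 11.3, 11.7.1). That stands too and limits the loss to subjects with no value in the window. The SAP's copy of the schedule appears to have no Week 2 KHQ or OABSS, so MMRM may have only Week 6 to draw on.

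The endpoints are supportive. They have no multiplicity control, only two of nine KHQ domains are tested, and PVR has no p-value. The PVR risk is also shown by PVR categories, catheterization and urinary retention summaries (SAP 8.5). By-visit ANCOVA is a conventional choice.

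That the simulated bias is toward zero is only partly reassuring. The direction belongs to the mechanisms simulated: if poor responders left the active arm only, it would reverse. For PVR, attenuation would understate a safety effect.

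Three stronger readings are tempting but not supported:
- **Questionnaire gaps are more frequent than diary gaps.** SAP 11.6.3 says "If missing data exists in KHQ and OABSS data in the visit, the corresponded item or domain will be treated as missing", while a diary visit needs only one valid day. But Protocol 7.3.1.2 has site staff ensure that all questions are answered, and the diary is itself not collected during urinary tract infection symptoms (Protocol 7.3.1.1).
- **The PVR effect is understated by a calculable amount.** The 7.1% in Protocol 4.6.1 is an overseas rate of the urinary retention adverse event, from pooled data that include an extension study. It is not a share of subjects who leave. Raised PVR is not a listed withdrawal criterion (Protocol 5.5), and Protocol 7.4.7 provides follow-up for these subjects within the study.
- **Every continuous diary endpoint uses MMRM.** Percent changes are only summarised (SAP 2.1).

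**Conclusion.** The inconsistency is in both documents and is unexplained. Its consequence is conditional: the Week 12 contrasts for OABSS total, KHQ role and social limitations, and PVR can be biased if missingness depends on the earlier response. A reader might infer that these results will be biased, or that patient-reported benefit will be materially distorted. The documents do not support that, because they give neither a dropout rate nor evidence that dropout relates to response.

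Under the most neutral form of response-related dropout simulated (equal dependence, 5% to 10%), the bias is about 0.01 to 0.03 SD, well below one standard error. It grows if dependence differs by arm and vanishes if dropout is unrelated to response. These sizes rest on the assumed effect, correlation, slopes and dropout rates, and the simulation represents a standardised score, not PVR in mL. The MMRM result holds under missing at random. The change is worth making because it is nearly free and uses the plan's own model. The primary and major secondary conclusions are unaffected.

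**What to change.** In Protocol 9.4.2 and SAP 7.3.5.1, analyse OABSS total and the two tested KHQ domains until Week 12 with the MMRM already specified for the major secondary endpoint. Its terms are treatment, site, stratum, visit, treatment-by-visit, baseline and baseline-by-visit, with unstructured covariance and Kenward-Roger. Keep by-visit ANCOVA after Week 12, as for the diary endpoints. For consistency, use the same model until Week 12 for the PVR estimate and confidence interval in SAP 8.5.1, still without a p-value. Record the change in SAP 2.1.

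The cost is SAP wording, reuse of an existing program and a changed layout for the tables up to Week 12. No additional data are needed.

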## **Safety**

All AEs that occur during the study will be recorded and classified using the current Medical Dictionary for Regulatory Activities (MedDRA). Events will be summarized overall, by treatment cycle and for the first 12 week of 1st treatment phase ( $\leq 84$  days from 1st treatment). Frequencies of AEs will be presented by system organ class and preferred term. Summaries of treatment-related AEs (study drug-related and injection procedure-related), AEs leading to discontinuation, AEs by intensity, and SAEs also will be provided.

ANCOVA for change from baseline in PVR urine volume will be performed at each visit. This model will include the treatment group, site and a stratification factor as fixed factors, baseline PVR urine volume as a covariate. The proportion of patients who will have a change from baseline in PVR

category (urine volume of < 100 mL, ≥ 100 to < 200 mL, ≥ 200 to < 350 mL, and ≥ 350 mL) will be summarized by visit.

The proportion of subjects using CIC (for urinary retention or elevated PVR) post-treatment will be summarized by PVR category. Time to start of CIC from most recent treatment, duration of CIC and PVR volume at the time of initiation of CIC will be also presented.

The observed value of clinical laboratory test and its change from baseline will be summarized by treatment group. The number of subjects with values outside of normal range by visit will be tabulated by treatment group to evaluate the changes in clinical laboratory tests.

The observed value of vital signs and changes from baseline will be summarized by treatment group. Also the ECG findings by visit will be summarized by treatment group.

## **10. STUDY GOVERNANCE CONSIDERATIONS**

### **10.1. Posting of Information on Publicly Available Clinical Trial Registers**

Study information from this protocol will be posted on publicly available clinical trial registers before enrollment of subjects begins.

### **10.2. Regulatory and Ethical Considerations, Including the Informed Consent Process**

Prior to initiation of a site, GSK will obtain favourable opinion/approval from the appropriate regulatory agency to conduct the study in accordance with ICH Good Clinical Practice (GCP) and applicable country-specific regulatory requirements.

The study will be conducted in accordance with all applicable regulatory requirements, and with GSK policy.

The study will also be conducted in accordance with ICH Good Clinical Practice (GCP), all applicable subject privacy requirements, and the guiding principles of the current version of the Declaration of Helsinki. This includes, but is not limited to, the following:

- IRB/IEC review and favorable opinion/approval of the study protocol and amendments as applicable
- Signed informed consent to be obtained for each subject before participation in the study (and for amendments as applicable)
- Investigator reporting requirements (e.g. reporting of AEs/SAEs/protocol deviations to IRB/IEC)
- GSK will provide full details of the above procedures, either verbally, in writing, or both.

